3.3 Overview of the DCS Device

Separate hybrid FDNIRS-DCS instruments are described in detail in the relative medical device brochure. FDNIRS-DCS devices are approximately 23" (l) x 18" (w) x 9" (h). Technical specs are provided at:

iss.com/biomedical/instruments/metaox.html. The devices are limited by Federal (or United States) law to investigational use. The devices contain no conductive patient leads and no user serviceable parts. They have a highest rated current of 3 Amp and are designed for safety compliance with UL/IEC 60601-1 3rd Edition as a Class I, Type B device. Prior to investigational use, devices are tested for conformance with ground bond, earth leakage, and enclosure leakage requirements. The devices are not yet under Food and Drug Administration (FDA) investigational device exemption (IDE) regulations, and are considered non-significant risk. During the conduct of human studies the investigators should follow good clinical practice requirements and 21 CFR 812 investigational device exemption regulations.

The FDNIRS portion of the instrument consists of 8 radio- frequency (110 MHz) modulated laser diodes operating at 8 different wavelengths ranging from 670-830 nm and 2 to 4 photomultiplier tube (PMT) detectors for heterodyne detection (similar to the Imagent from ISS, Inc).

The DCS component of the instrument consists of a long-coherence length 852 nm laser, 4 to 8 low dark-count photon counting avalanche photodiodes, and a custom-made correlator board. A short-pass filter in front of the FDNIRS PMTs, along with in-house designed software enables simultaneous FDNIRS-DCS measurements.

Furthermore, to customize this instrument for use in humans, the MGH group has designed optical probes which host fiber optics. Each probe consists of 1 source and up to 8 detector fiber bundles terminated with 90 deg prisms providing multiple source-detector separations (ranging from 0.3 to up to 5 cm).

The optical parameters for the FNIRS- DCS devices can be summarized as follows, irradiance 250-400 mW/cm²; area: 0.0962 cm² and 10 min exposure (twice 10 min, before and after the session with TPBM-1000); fluence: 150-240 J/cm². Total energy delivered in 10 min by the FNIRS-DCS devices: 14.43 – 23.08 J (this energy will be delivered twice before and after each TPBM-1000 sessions). The incremental exposure to NIR resulting from the FNIRS-DCS devices are minimal: in fact the NIR light is shed to a tiny area 1/350 of the area irradiated by TPBM-1000 and the energy shed in 10 min by the FNIRS-DCS are inferior to the total energy shed by the TPBM-1000 by more than 2 orders of magnitude.

3.1 Overview of the EEG Device

The StatX24 (Advance Brain Monitoring) is an internally battery powered Type BF device intended for continuous use (16-17 hours). The StatX24 provides an integrated approach for wireless acquisition and recording of electroencephalographic (EEG), electrooculographic (EOG), and electrocardiographic (ECG) signals. The system

utilizes the patented Sensor Headset and patented EEG sensors, which record high quality EEG, obtained with less than five-minutes of set-up time and no scalp abrasion required. The wireless technology allows the user to be un-tethered and move around the home, healthcare facility, or clinical research environment while real time data is collected and displayed.

The StatX24 acquires twenty channels of monopolar EEG recordings with a linked mastoid reference and optional channel for ECG, EOG, or EMG. The 1-10th channels, as well as the 21st channel, are differential channels. The 22nd-24th channels are referential channels. The StatX24 consists of: (1) StatX24 Headset with a Bluetooth (BT) Receiving Unit for bi-directional transmission of digitized physiological signals, (2) a Neoprene Strap, and (3) a Strip with EEG sensors sites in the standard 10-20 format + POz (Fz, Cz, Pz, F3, F4, C3, C4, P3, P4, O1, O2, T5, T3, F7, Fp1, Fp2, F8, T4, and T6 with Linked Mastoids).

The Sensor Headset collects signals from the sensors placed on the patient and performs analog-to-digital conversion, encoding, formatting, and transmitting of all signals. The signals communicate using a 2.4 to 2.48 GHz radio transmitter. StatX24 acquisition utilizes the bi-directional capabilities of the system to initiate scalp-electrode impedance monitoring and monitors the battery capacity in the StatX24 Headset. A BT Receiving Unit is used as the base unit affixed to the PC workstation.

3.2 Overview of Rationale for Diffuse Correlation Spectroscopy Cognitive Tasks and Electroencephalogram

Diffuse Correlation Spectroscopy

4.1 Rationale

The specific aims of this study are:

1. To assess the change in cerebral blood flow induced by the Transcranial Continuous and Pulse Near-Infrared Light Therapy (c-TLT and p-TLT) in healthy subjects
2. To correlate with cognitive performance the change in cerebral blood flow induced by the Transcranial Continuous and Pulse Near-Infrared Light Therapy in healthy subjects
3. To correlate with brain electrical activity the change in cerebral blood flow induced by the Transcranial Continuous and Pulse Near-Infrared Light Therapy in healthy subjects
4. To correlate with skin pigmentation the change in cerebral blood flow induced by the Transcranial Continuous and Pulse Near-Infrared Light Therapy in healthy subjects
5. To assess the safety and tolerability of the Transcranial Continuous and Pulse Near-Infrared Light Therapy in healthy subjects

4.2 Study Design

This study is a single-blind, sham-controlled, study on the use of Transcranial continuous light therapy (c-TLT) and pulse light therapy (p-TLT) as an enhancer of cerebral blood flow in healthy subjects.

We expect that out of 30 subjects enrolled 10 subjects will be eligible to complete a sequence of three sessions of Transcranial Light Treatment (TLT) and sham.

All eligible subjects will receive two TLT sessions and one of sham (s-TLT) within the course of 5 weeks. While the sequence (c-TLT, s-TLT, p-TLT) will be the same for all subjects, the subjects will be blind to the specific mode of function used in each session.

The study site (MGH) will have one Litecure device, which will recognize the subjects' codes generated by the study statistician. Only subjects will be blind to the treatment group assignment. The Sham treatment consists of applying all the procedures for the delivery of the TLT, while actually delivering no light. The blinding of the sham will be effective because the radiation is not visible and because the active therapy (continuous or pulsed) will not produce any subject-discriminable difference from sham, e.g., skin warming. The sham treatment will mimic the TLT procedure. The treatment will be bilateral and applied to the frontal areas with two application sites on the left side and two on the right side [left and right forehead centered on EEG sites on F3, F4, Fp1, Fp2]. Energy is administered with a radiation wavelength of 830 nm. The duration of irradiation is 20 minutes at each application site (the 4 sites are irradiated at the same time which is equivalent to 20 minutes of total time). The entire sessions is estimated to last about 1.5 hours. The additional time is needed to have the subject complete a urine toxicology and self-report forms, to prepare the subject, to place the necessary protections (e.g. goggles), to inspect the subject's skin, to complete DCS before and after TLT, to set the TLT devices, and to give the subject time to rest after the irradiation. TLT treatment will only be administered by licensed physicians (i.e. MDs) who are on study staff. All staff who deliver treatment must pass training that is approved by the MGH Laser Safety Committee. The treatment will follow these specifications: wavelength 830 nm; average irradiance 54.8 mW/cm²; average fluence of 65.8 J/cm² (consistently with energy density used in the ELATED-2 study at MGH with the device Omnilux New U).

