5.7 ADDITIONAL SAFETY ANALYSES	31
6 ETHICAL REVIEW & REGULATORY CONSIDERATIONS.....	32
6.1 ETHICAL REVIEW.....	32
6.2 REGULATORY CONSIDERATIONS.....	32
6.3 MONITORING PROCEDURES.....	32
6.3.1 Training of Study Site Personnel	33
6.4 INFORMED CONSENT.....	33
6.5 PROTOCOL ADHERENCE.....	33
6.6 DATA COLLECTION	33
6.7 RECORD RETENTION	34
6.8 CLINICALTRIALS.GOV.....	34
7 REFERENCES	35
8 LIST OF PROTOCOL ATTACHMENTS.....	38
8.1 PROTOCOL ATTACHMENT 1 – TIME TABLE OF STUDY PROCEDURES.....	38
8.1 PROTOCOL ATTACHMENT 2 – SCHEMA	39

Transcranial Near-Infrared Light in Healthy Subjects: a Cerebral Blood Flow Study with Diffuse Correlation Spectroscopy (NIR-flow).

1. Study Summary

Protocol #:

Study Purpose: The purpose of this study is:

- To assess the change in cerebral blood flow induced by the Transcranial Continuous and Pulse Near-Infrared Light Therapy in healthy subjects
- To correlate with cognitive performance the change in cerebral blood flow induced by the Transcranial Continuous and Pulse Near-Infrared Light Therapy in healthy subjects
- To correlate with skin pigmentation the change in cerebral blood flow induced by the Transcranial Continuous and Pulse Near-Infrared Light Therapy in healthy subjects
- To correlate with brain electrical activity the change in cerebral blood flow induced by the Transcranial Continuous and Pulse Near-Infrared Light Therapy in healthy subjects
- To assess the safety and tolerability of the Transcranial Continuous and Pulse Near-Infrared Light Therapy in healthy subjects

Trial Design: In essence, this study consists in three sequential sessions of Diffuse Correlation Spectroscopy (DCS), each one week apart, to test three different modes of intervention with Transcranial Light Therapy (TLT). Healthy subjects will receive first a session with continuous light (c-TLT), then a session with sham (s-TLT) and one session with pulse light (p-TLT). Before and after each session, subjects will undergo DCS, which will allow measuring the impact of the intervention on cerebral blood flow. We expect that out of 30 subjects enrolled 10 subjects will be eligible to complete the study. The study will be conducted in single blind.

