4.8.2 TLT-DCS Visits – Visits 2-4 (Weeks 2-4)

The TLT sessions will occur once weekly for three weeks at the MGH Martinos Center for Biomedical Imaging in Charlestown. Subjects missing one session will be allowed to still receive their TLT session, by shifting the overall study schedule of one week. The study PI will be an active participant in the delivery of the TLT. The PI and other collaborators from MGH CATSD will assist with the delivery of TLT. The device TPBM-1000 for the administration of the TLT will be provided by Litecure Inc. Litecure will provide training of MGH CATSD staff in the use of the device and will provide training certificates at the completion of the training.

The overall study visit is estimated to last about 1.5 hours. The TLT session is estimated to last about 50 min – 5 minutes of EEG before DCS, 10 minutes of DCS before TLT, 20 minutes of TLT, 10 minutes of DCS after TLT and 5 minutes of EEG after DCS. EEG recording will extend to cover at least part of the time devoted to the cognitive tasks. Study sessions will take place in an office dedicated to TLT treatment at MGH Martinos Center for Biomedical Imaging in Charlestown. Only the subject and the staff administering the TLT will be allowed in during the session. The subject will comfortably lie down on an exam bed or sit on a recliner. The sites of application of TLT (left and right forehead) will be inspected for any possible skin lesions (e.g. laceration or signs of inflammation) which would contraindicate the treatment. The study staff administering the TPBM device at the TLT-DCS sessions will appropriately remove any reflective objects to fall into or obstruct the path of the light energy produced by this device. Both the subject receiving the TLT and the study staff will wear protective eyewear in the form of goggles. During treatment sessions the office will be kept completely dark and a warning sign will hang at the office door. The staff will be provided training on basic safety procedures relative to the use of the device.

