The trained staff administering the TLT will use utmost care to never shine the light in or near the eyes of the subject safety goggles will be selected based on the TLT biophysical properties, in accordance to the Occupational Safety and Health Administration (OSHA) guidelines. The delivery of the TLT is expected to last 20 min total (simultaneous application on the left and right forehead). The subject will be asked to rest for five minutes after the delivery of TLT. The skin at the sites of the application will be inspected again prior to dismissing the subject. A log with the dates of treatment delivery per each study subject will be kept at MGH CATSD (Boston).

During TLT-DCS Visit 2-4, subjects will receive TLT-c (Visit 2), TLT-s (Visit 3) and TLT-p (Visit 4).

The following tasks will be completed prior to every TLT session:

- Utox
- Concomitant medications form
- ADVERSE EVENTS FORM
- ASQ (self-rated)
- SDQ (self-rated)
- NEURO-QoL (self-rated)
- SFI (self-rated)
- SAFTEE (self-rated)
- PANAS (self-rated)
- EEG- Recording
- DCS – Spectroscopy

The following tasks will be completed after every TLT session:

- DCS – Spectroscopy
- EEG- Recording
- Cognitive tests
- PANAS (self-rated)
- TSRQ (self-rated)
- PBQ (self-rated)

Subjects shall be instructed to contact the investigator or a member of his staff at any time between visits concerning adverse events or worsening of symptoms.

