5.2 Specific Primary Aim

To assess the change in cerebral blood flow induced by the Transcranial Continuous and Pulse Near-Infrared Light Therapy in healthy subjects

Hypothesis 1: We anticipate that p-TLT will trigger a significantly greater increase in CBF as compared to c-TLT, and c-TLT will trigger a significantly greater effect than sham (s-TLT). We expect that we will be also able to estimate the effect size of each type of TLT in terms of increase of CBF.

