5.5 Efficacy Analyses for Primary Aims

For the primary analysis, delta CBF (measured with DCS-spectroscopy pre- and post-TLT) will be compared in all ten subjects by paired t-test. The primary comparisons will include: a) delta CBF for p-TLT and delta CBF for c-TLT subjects (n=20 within subject comparison) and b) delta CBF for c-TLT and delta CBF for s-TLT (n=20 within subject comparison).

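### One fixed session order for every subject makes both primary CBF contrasts inseparable from visit number

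*Combined protocol and SAP*

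**What the plan says.** Section 4.2 (Study Design) sets one order for everyone: "While the sequence (c-TLT, s-TLT, p-TLT) will be the same for all subjects". The Study Summary, section 4.8.2 and the schema in the attachments agree: continuous light (c) at Visit 2, sham (s) at Visit 3, pulsed light (p) at Visit 4. On spacing, section 4.8.2 says "The TLT sessions will occur once weekly for three weeks".

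Hypothesis 1 in section 5.2 is that "p-TLT will trigger a significantly greater increase in CBF as compared to c-TLT, and c-TLT will trigger a significantly greater effect than sham"; the section also aims to estimate an effect size for each type of light. For the primary analysis, section 5.5 says "delta CBF (measured with DCS-spectroscopy pre- and post-TLT) will be compared in all ten subjects by paired t-test", with two primary comparisons, p versus c and c versus s. It has no visit or period term, and the plan does not discuss order or carry-over. Section 4.5 refers once to data after randomisation, but no randomisation is described anywhere.

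**The concern.** When each mode is given at only one visit, a difference between modes is also a difference between visits. Taking post minus pre within a session removes a visit shift in the CBF level. It does not remove a visit effect on the change itself, such as habituation after a first session in an unfamiliar setting. Sham cannot act as the control for this, because it is only ever given at Visit 3. A change in measurement technique on a calendar date is a lesser problem: it confounds only subjects whose sessions straddle that date.

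In addition, every sham session follows a c-TLT session by about a week, so any carry-over from c-TLT falls on sham in every subject.

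At stake is whether either part of Hypothesis 1, or any effect size estimated for the two light modes, can be attributed to the mode of light.

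**Working it through.** **Inputs.** Order and visits: sections 4.2 and 4.8.2. Contrasts and test: section 5.5. Ten treated subjects: section 5.1. The documents give no SD, alpha, sidedness or power; two-sided 5% is assumed, and shifts are expressed in SDs of the paired difference.

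**The plan's own figure.** Section 5.5 gives n=20 per contrast: 10 subjects × 2 sessions = 20 values, that is 10 pairs and 9 df. This reproduces. There is no power figure to reproduce.

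**1. What the contrasts estimate.** Let v2, v3 and v4 be visit effects on delta CBF. In the fixed order:

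- E[p − c] = (p − c) + (v4 − v2)
- E[c − s] = (c − s) + (v2 − v3)

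**2. Identifiability.** The model has 10 subject + 2 mode + 2 visit = 14 columns. In the fixed order its rank is 12, and the rank is already 12 without the visit columns, so both visit df coincide with the two mode df. With all six orders in use the rank is 14 of 14.

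**3. Illustrative size for one contrast, no mode effect.** Noncentral t, 9 df, noncentrality = shift × √10.

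| Shift (SD) | False rejection |
|---|---|
| 0.1 | 5.9% |
| 0.25 | 10.9% |
| 0.5 | 29.3% |
| 1.0 | 80.3% |

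A linear drift of d per visit adds +2d to p − c and −d to c − s. With d = 0.25, the rates are 29.3% and 10.9%.

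**4. Both parts of Hypothesis 1 falsely significant together** (simulation, n=10, equal independent errors, 400,000 runs per pattern):

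- First-session effect of 0.25, 0.5 or 1.0 SD, either sign: at most 0.003%. Singly, a higher Visit 2 gives false c > s in 10.6%, 29.4% and 80.3%; a lower Visit 2 gives false p > c in 10.6%, 29.3% and 80.3%.
- Linear trend of 0.25 SD per visit: about 0.01% or less.
- Visit 3 lower and Visit 4 higher than Visit 2, each by 0.25, 0.5 or 1.0 SD: 0.2%, 4.5% and 62.3%.

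**5. Carry-over.** Suppose an active session adds k, of either sign, to the next session's delta. In the fixed order only sham follows an active session, so c − s is biased by −1.0k and p − c by 0. The residual bias with six orders and visit adjustment is:

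| Subjects lost | c − s | p − c |
|---|---|---|
| 0 | −0.22k to −0.43k | −0.15k to +0.15k |
| 1 | −0.11k to −0.57k | ±0.30k |
| 2 | 0 to −0.61k | ±0.44k |

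**6. Price of randomising.** Ten subjects over six orders, each used once or twice, gives 15 allocations. Each contrast's paired difference is regressed on visit terms. Power is at an assumed true difference of 1.0 SD.

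| Subjects lost after assignment | df | Extra variance | Power | Paired t-test power |
|---|---|---|---|---|
| 0 | 7 | 0-7% | 74.6-77.4% | 80.3% |
| 1 | 6 | 0-27% (median 3%) | 60.5-70.7% | 74.8% |
| 2 | 5 | 0-100% (median 9%) | 36.8-62.3% | 68.1% |

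Both contrasts stay estimable in every one of these patterns. The loss rows remove whole subjects; partial completers were not modelled.

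**7. Calibration** (200,000 runs, no mode effect). With the p-TLT SD doubled, one pooled model rejects p versus c in 7.8-7.9% and c versus s in 1.0-1.1%. The contrast-specific regressions reject in 5.0-5.1%, and in 4.9-5.0% under a trend of 0.5 SD per visit.

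**The case against.** The strongest reply is that no bias has been shown. This is a small mechanistic study, the documents give no visit effect or SD, and every rejection rate above rests on an assumed shift. A linear trend or a first-session effect pushes the two contrasts in opposite directions, so it would almost never make the whole of Hypothesis 1 falsely significant. That is correct and limits the claim. It does not remove it: section 5.5 makes each contrast primary, each can be read alone, and the data cannot show which visit pattern held. Blinding of subjects does not help, because everyone has the same order.

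The case for carry-over is thin. Section 4.8.3 plans a look at lasting cognitive effects one week after the last session, and the study cited for a CBF response after one session carries a title about psychological benefit at two and four weeks. Neither is evidence on CBF in healthy subjects. A residual shift in level that is stable through the session also cancels in the delta. Carry-over is therefore possible, not shown. If k is positive, it works against finding c > sham.

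Randomising has a price for p versus c. The fixed order gives that contrast no first-order carry-over bias, whereas six orders leave some, and more if subjects are lost. Finally, once orders are randomised the plain paired t-test is valid, though conservative: it rejected in about 2-4% of simulated trials with visit effects. Visit adjustment is thus a refinement; randomisation is the essential step.

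**Conclusion.** The concern holds and should be fixed before enrolment. Both primary contrasts are completely aliased with visit number (rank 12 of 14). Attributing either to mode requires assuming no visit-number effect on delta CBF and, for c versus s, no carry-over. These data cannot test that assumption, and more subjects in the same order would not help.

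This is non-identifiability, not a demonstrated bias. Confidence is high for the aliasing, which follows from the design alone. It does not extend to the size or direction of any bias: the rejection rates of 5.9% to 80.3% rest on assumed shifts of 0.1 to 1.0 SD, 10 pairs and a two-sided 5% test.

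**What to change.** 1. Randomise subjects as evenly as possible over the six orders of c, sham and p, keeping the number and spacing of sessions. Section 4.2 says the device recognises "codes generated by the study statistician". That these could carry a per-visit order is an inference to confirm with the manufacturer.
2. Assign the order at Visit 2, so that screen failures and drop-out before the first session (section 4.4) do not unbalance it.
3. Analyse each primary contrast separately: regress the subject's paired difference on visit terms and test the intercept against that contrast's own error, not a pooled equal-variance error.
4. Prespecify a sensitivity analysis with first-order carry-over terms, fitted to all three sessions with mode-specific variances. Separate c and p terms cost 18-38% more variance (14 df) if variances are equal; the mode-specific-variance version was not calibrated. In the paired-difference regression the same terms need 2.5 to 5.0 times the variance (5 df), too weak to use.
5. Reconcile the mention of randomisation in section 4.5 with the design adopted.

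**Cost.** A protocol amendment and a randomisation list, and about 3 to 6 points of power at 1.0 SD with 10 completers (80.3% to 74.6-77.4%). Losses after assignment cost more, but section 4.8.2 limits them: "Subjects missing one session will be allowed to still receive their TLT session, by shifting the overall study schedule of one week".

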4.3 Study Population

Healthy subjects who meet all inclusion criteria, have none of the exclusion criteria, and are willing to undergo the Informed Consent process will be eligible to participate in this study.

4.3.1 Population Description

The subject population for this study will consist of healthy subjects between the ages of 18 and 70, of any ethnic background. We expect to enroll 30 subjects in order to have 10 who are eligible and complete the study. The subject will meet all the inclusion criteria, have none of the exclusion criteria, and provide their written Informed Consent to participate in this clinical study. In the event that a subject's ability to comprehend and communicate is compromised (per the assessment of the Investigator), local regulations pertaining to Informed Consent signatures should be followed.

Subjects will be recruited, via screenings, advertisements, and postings. Study participants will also be recruited via internet-based advertisements, e.g., Craigslist, Clinical Trials @ Partners, the study site's websites, RSVP for Health (which will also generate listserv emails to Partners employees, regarding research studies in need of volunteers), etc.

Participants who contact the respective study site staff in response to any of the aforementioned advertisements will complete phone screening questions to determine preliminary eligibility for the study.

